#### Chronic Pain

**Trends in endpoints.** In addition to the primary and secondary endpoints described above, we will compare the time trends in the endpoints: pain control, pain reduction, clinically significant pain reduction, and opioid misuse score at baseline, 1, 3, and 6 months among the CYP2D6 IM or PM subgroup, using a repeated-measures mixed effect model or generalized repeated-measures mixed effect model, as appropriate. Since participants are randomized to Intervention and Control groups and not to the CYP2D6 IM or PM subgroup within Intervention and Control groups, there could be important differences in baseline characteristics between the two groups. For these reasons, we will conduct covariate-adjusted repeated measures mixed models that will account for differences in baseline characteristics that differ between the Intervention – CYP2D6 IM or PM subgroup and the Control – CYP2D6 IM or PM subgroup. Potential baseline characteristics may include age, sex, income, education, insurance, and medical conditions. We will select the appropriate covariance matrix (e.g. compound symmetry, autoregressive, unstructured, or other covariance structure) based on the data.

**Difference within the NM group.** In the control arm participants, we will compare pain scores and pain control in participants with a CYP2D6 activity score  $>0.75 - 1$  to participants with an activity scores  $>1-2$  using a two-sided two-sample t-test or Mann Whitney test, as appropriate, with a type 1 error of 0.05. Additionally, we will use linear regression to adjust for differences in baseline characteristics.

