**Chronic Pain:**

**PROMIS pain intensity scale** – A participant completed 3-question survey of average pain over the last 7 days, worst pain over the last 7 days, and current pain. Each question is on a 1-5 integer scale, the

higher the value, the more intense the pain. This survey will be administered at baseline, 1 month, 3 months, and 6 months post return of results.

*PROMIS prescription pain medication mis-use scale* - A participant completed survey of prescription medication misuse over the past 30 days. The survey is comprised of 7 questions on a 5-point ordinal scale of never/rarely/sometimes/frequently/almost always or not at all/a little bit/somewhat/quite a bit/very much[33]. This survey will be administered at baseline, 3 months, and 6 months post return of results.

*PROMIS emotional distress depression 8b survey* - A participant completed eight question survey assessing frequency of depression symptoms over the past 7 days[36]. This survey will be administered at baseline, 1 month, 3 months, and 6 months post return of results to the adult participants.

*Opioid side effects* – A participant completed survey of common opioid side effects experienced and the extent to which those side effects bothered the participant. This survey will be administered at baseline, 3 months, and 6 months post return of results to the adult participants.

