### 11.2 Data Element Definitions

Clinically significant pain reduction: Whether or not the pain reduction score is  $\leq 0.7$ . If the pain reduction score is  $\leq 0.7$ , clinically significant pain reduction is achieved, if pain reduction scores is  $> 0.7$ , clinically significant pain reduction is not achieved.

Depression symptom control: The change in the PROMIS Emotional Distress - Depression 8b or PROIMIS pediatric Depression 8a survey depression score from baseline to time t.

Depression remission: A. Whether or not the summed raw PROMIS emotional distress depression 8b survey responses are  $\leq 16$ , which is equivalent to the participant responding “rarely” or “never” to most or all of the PROMIS emotional distress - depression 8b survey questions. B. Whether or not the PHQ-8 scores are  $\leq 4$ , which is equivalent to depression severity being none-mild.

Depression (PHQ-8) score: The sum of the responses to the PHQ-8 survey, range from 0 to 24.

Depression (T) score: The T-score converted summed responses to the PROMIS emotional distress depression 8b survey. The T-score conversion is centered around 50 with standard deviation of 10.

Depression severity: The depression score converted to depression severity (none, mild, moderate, severe) based on the scoring guide for the PROMIS emotional distress depression 8b survey.

Medication adherence: The scored responses to the Voils Medication Adherence survey.

Medication concordance: Whether or not the medication the participant is prescribed after the intervention is concordant with the participants CYP2D6 and, for the depression trial, CYP2C19 phenotype.

Medication side effects severity burden: (Depression only) The sum of the scored severity (none = 0, mild = 1, moderate = 2, severe = 3) for common SSRI side effects.

Opioid misuse score: The T-score converted summed responses to the PROMIS prescription medication misuse 7a survey. The T-score conversion is centered around 50 with standard deviation of 10.

Opioid persistence: Defined as  $\geq 1$  opioid prescription refill between 90 days and 180 days after the surgical procedure.

Opioid usage: The average daily morphine equivalents in mg (MED) in past 7 days. MEDs will be calculated using data from the opioid usage survey.

Overall well-being: Defined as the T-score converted summed responses to the PROMIS 43/PROMIS 37 pediatrics survey. The T-score conversion is centered around 50 with standard deviation of 10.

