Pain control: The difference in pain intensity score at follow-up time t and the baseline pain intensity score.

Pain intensity score: The mean of average pain in the last 7 days, current pain, and worst pain in the last 7 days. Average pain, current pain, and worst pain will be collected using the 3-question PROMIS pain intensity scale.

Pain reduction score: The ratio of the pain intensity score (derived from the PROMIS pain intensity survey) at follow-up time t to the baseline pain intensity score.

Silverman integrative analgesic assessment (SIA) score: This is an integrated measure of pain and opioid usage, calculated as follows: pain and opioid usage are ranked, the ranks are converted to percentiles and linearly transformed such that the scores are centered at 0 and range -100 to 100. The pain scores and opioid usage transformed percentiles are summed to generate the SIA score that ranges -200 to 200. Negative values indicate low pain with minimal opioid usage, while positive values indicate higher pain with higher opioid usage. See Appendix A for additional details and supporting rationale.

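### The chronic pain trend models list baseline as a visit for three endpoints that are constant there, which rules out one named covariance structure and understates the error of single-visit arm comparisons

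*Combined protocol and SAP*

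**What the plan says.** Section 10.6 (Chronic Pain, Trends in endpoints) compares time trends in the actionable subgroup for "pain control, pain reduction, clinically significant pain reduction, and opioid misuse score at baseline, 1, 3, and 6 months", "using a repeated-measures mixed effect model or generalized repeated-measures mixed effect model, as appropriate". The covariance matrix is to be chosen from the data; compound symmetry, autoregressive and unstructured are named as examples. The same paragraph plans covariate-adjusted versions, because the actionable subgroups were not themselves randomized and may differ at baseline.

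Section 11.2 defines the four endpoints:

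- Pain control: "The difference in pain intensity score at follow-up time t and the baseline pain intensity score".
- Pain reduction: "The ratio of the pain intensity score (derived from the PROMIS pain intensity survey) at follow-up time t to the baseline pain intensity score".
- Clinically significant pain reduction: "Whether or not the pain reduction score is" at most 0.7.
- Opioid misuse score: "The T-score converted summed responses to the PROMIS prescription medication misuse 7a survey". This is a level at the visit, not a change.

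On the pain intensity items, section 7.3 states: "Each question is on a 1-5 integer scale". A baseline score of zero cannot occur, so the ratio is always defined.

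**The concern.** Three of the four endpoints carry no information at baseline, because each participant is compared with himself or herself. A visit with zero variance does not suit the covariance structures that the section names. One of them cannot be fitted at all. The others can be fitted, but the zero enters the variance used for later visits.

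The trend models are also where section 10.6 places covariate adjustment, while the primary chronic pain test in section 10.4 is unadjusted. An adjusted arm difference at month 3, the primary timepoint, is a natural figure to report beside the primary result. It is also the kind of estimate whose standard error is affected.

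**Working it through.** **Sample size used.** The trend models have no size of their own, so the section 10.1 figure was reproduced first. With effect 0.40 SD, two-sided alpha 0.049 and 90% power, the normal approximation gives 2 × (1.969 + 1.282)² / 0.40² ≈ 132.1, so 133 per arm. The exact t calculation gives 134 per arm (power 90.2%), which matches the plan's 134 + 134 = 268.

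**Values at baseline.** Putting baseline into the section 11.2 definitions:

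- pain control = baseline − baseline = 0
- pain reduction = baseline / baseline = 1
- responder status: 1 > 0.7, so not achieved

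These hold for everyone in both arms. The opioid misuse score does vary at baseline.

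**Unstructured covariance.** The baseline row and column are zero. The 4 × 4 matrix has rank 3 and determinant 0, so it cannot be fitted.

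**Responder model.** With categorical visit there are 0 events at baseline in both arms. In a simulated data set of 134 per arm, both logistic regression and GEE returned standard errors above 10,000 for the intercept, visit and arm terms, and for the arm-by-visit terms referenced to baseline.

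**Compound symmetry, arm difference at one visit.** The model uses one variance for all visits. If change has variance s² at each of the three follow-up visits, the pooled value is (0 + 3s²)/4 = 0.75s².

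- Standard error ratio: √0.75 = 0.866, or 13% too small. At 134 per arm this is 0.106s against a true s√(2/134) = 0.122s.
- Type I error: 2 × (1 − Φ(1.96 × 0.866)) = 2 × (1 − Φ(1.697)) = 9.0%.

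**Simulation under no effect.** The following are assumptions, not figures from the documents: pain intensity with mean 3.4 and SD 0.8, rounded to thirds and held within 1–5, under three correlation patterns (constant 0.5; decay of 0.85 per month; weaker correlation with baseline). There were 20,000 runs per setting for compound symmetry and 5,000 for AR(1). Rejection rates at nominal 5% with baseline included, as ranges over the three patterns:

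| Endpoint | Fitted structure | Arm-by-time | Month-3 arm difference |
|---|---|---|---|
| Pain control | Compound symmetry | 5.0–6.4% | 9.0–9.3% |
| Pain control | AR(1) | 5.8–6.2% | 9.1–10.8% |
| Pain reduction | Compound symmetry | 5.0–6.8% | 8.8–10.0% |
| Pain reduction | AR(1) | 5.1–7.0% | 8.4–10.9% |

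The arm main effect rejected 4.7–5.2% of the time under compound symmetry and 3.9–7.8% under AR(1).

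**Why the trend test largely survives.** Subtracting baseline leaves contrasts between a person's own visits unchanged. For pain control under compound symmetry, the arm-by-time F statistic equals that of the raw-score model (0.2160 and 0.2160 in one data set). Any excess over 5% there is shared by the raw-score model, so it comes from a misspecified covariance and not from the constant visit.

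**With baseline removed.** In 3,000 runs per setting (Monte Carlo error about ±0.8 points), arm-by-time rejected 4.1–5.5% and the month-3 difference 4.3–6.2% over compound symmetry, AR(1) and unstructured fits. The unstructured matrix could be estimated. Raw pain intensity with baseline kept, run for the constant and weaker-baseline patterns, gave about 5–6%.

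**The case against.** The strongest reply is that section 10.6 sets out to compare time trends. That most naturally means the arm-by-time test, which stays near its level; a single-visit difference is not named. This stands, and it limits the finding. It does not remove it, because the contrast is left unspecified and month 3 is an obvious one to report.

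For the responder endpoint, separation is confined to the baseline cells. In 300 simulated logistic fits with arm-by-visit terms, the month-3 arm log-odds ratio and its standard error agreed with and without the baseline rows to within 3 × 10⁻⁷. This also stands when visit is categorical. Contrasts against baseline remain unusable.

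It can further be said that section 11.2 defines the change and the ratio only at a follow-up time, and that the visit list is shared wording that cannot be literal for every endpoint. Opioid misuse, for instance, is not collected at 1 month (section 7.3 and Table 8). On that reading baseline is not a modelled visit for the derived endpoints. It is a plausible intention, but the text does not say it.

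The data-based covariance choice and the separate SAP promised in sections 10.2 and 10.6 might catch the problem. Nothing in these documents drops the baseline row.

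A reader might infer that the trend models break down altogether, or that the error rate of the chronic pain trial is compromised. Neither follows. A compound-symmetry model of pain control can be fitted and gives a usable trend test, section 10.8 calls the repeated-measures analyses exploratory, and the tests in sections 10.4, 10.5 and 10.7 do not use them. The synopsis also lists covariate adjustment separately from time trends, so adjustment need not rest on these models alone.

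**Conclusion.** The point holds in a limited form and is minor. As written, the visit list includes a constant for three of the four chronic pain trend endpoints. Three consequences follow:

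- The unstructured option cannot be used.
- The responder model separates in its baseline cells.
- For pain control and pain reduction, a single-visit arm difference from a compound-symmetry or AR(1) fit has a type I error of about 8–11% instead of 5%.

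The 13% and 9.0% figures assume compound symmetry and equal variance of change at the three follow-up visits. The simulated ranges rest on the assumed score distribution and the three correlation patterns. The 5–7% for arm-by-time applies to pain control and pain reduction, not to the responder endpoint.

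The acute pain and depression trend paragraphs list scores or levels at each visit, so they do not share the problem.

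**What to change.** Amend the trends sentence in section 10.6 (Chronic Pain), and carry the same text into the trial-specific SAP, in one of two ways:

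- Model pain control, pain reduction and clinically significant pain reduction at 1, 3 and 6 months only, with baseline pain intensity as a covariate.
- Model the raw pain intensity score at baseline, 1, 3 and 6 months, and derive change from the fitted visit means. If responder status is kept as a trend endpoint, model it at the follow-up visits only.

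In either case, state whether visit is categorical and name the contrast: arm-by-time, the month-3 arm difference, or both. In the same edit, limit the opioid misuse visits to baseline, 3 and 6 months, to agree with section 7.3 and Table 8.

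The cost is about one sentence. No new data are needed, and nothing changes in the primary, secondary or interim tests or in the sample size.

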Study Population	
Acute Pain  Randomized Population  Approximately 1730* participants with planned/elective surgery who are anticipated to start a paincontrol medication with existing CPIC guidelines after their surgery
 
Analytical Population  Approximately 304 participants from the randomized population who have an actionable phenotype defined as CYP2D6 IM or PM (i.e. CYP2D6 activity score <math>\leq 0.75</math>)
 
Chronic Pain  Randomized Population  Approximately 985* participants see in primary care or pain specialty clinics who are already prescribed or anticipated to be prescribed tramadol, codeine, or hydrocodone for pain control.
 
Analytical Population  Approximately 268 participants from the randomized population who have an actionable phenotype defined as CYP2D6 IM or PM (i.e. CYP2D6 activity score <math>\leq 0.75</math>)
 
Depression  Randomized Population  Approximately 1540* participants seen in primary care or psychiatry clinics who are already prescribed or anticipate to be prescribed an SSRI with existing CPIC guidelines
 
Analytical Population  Approximately 542 participants from the randomized population who have an actionable phenotype, defined as a CYP2D6 PM or ultra-rapid metabolizer (UM), or a CYP2C19 PM, rapid metabolizer (RM), or UM

	*Subject to change based on the actionable phenotype rates and missing data.
Number of Sites	11 sites with approximately 60-80 clinics
Duration of Subject Participation:	Up to one year from consent to end of follow-up

Description of implementation of intervention (e.g.,	The intervention for ADOPT PGx is the immediate return of PGx testing results to the participant's healthcare provider.

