#### **4.1 Randomization**

After participants provide informed consent/assent, participants will be randomized in a 1:1 allocation to the Intervention (i.e. immediate PGx testing and genotype-guided opioid or SSRI therapy with clinical decision support) and Control (i.e. usual care with delayed PGx testing) arms. Randomization will be stratified by trial and site or clinic with a random block size within each site or clinic. We anticipate variability in patient populations between recruiting sites or clinics and aim to balance the intervention assignments within the site or clinic unit. Additionally, the randomization for the chronic pain trial will be stratified by presence/absence of depression, and the randomization for the acute pain and depression trials will be stratified by pediatric/adult.

The randomization scheme will be generated by an unblinded statistician. Randomization assignments will be generated in real time in REDCap at the Coordinating Center.

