#### Acute Pain

**Trends in endpoints.** In addition to the primary and secondary endpoints described above, we will compare the time trends in the endpoints: pain scores, opioid usage, opioid misuse score, and mobility score at baseline, 1, 3, and 6 months among the CYP2D6 IM or PM subgroup, using a repeated-measures mixed effect model or generalized repeated-measures mixed effect model, as appropriate. Since participants are randomized to Intervention and Control groups and not to the CYP2D6 IM or PM subgroup within Intervention and Control groups, there could be important differences in baseline characteristics between the two groups. For these reasons, we will conduct covariate-adjusted repeated measures mixed models that will account for differences in baseline characteristics that differ between the Intervention – CYP2D6 IM or PM subgroup and the Control – CYP2D6 IM or PM subgroup. Potential baseline characteristics may include age, sex, income, education, insurance, surgical procedure type. We will select the appropriate covariance matrix (e.g. compound symmetry, autoregressive, unstructured, or other covariance structure) based on the data.

**Difference within the NM group.** In the control arm participants, we will compare pain scores in participants with a CYP2D6 activity score  $>0.75 - 1$  to participants with an activity scores  $>1-2$  using a two-sided two-sample t-test or Mann Whitney test, as appropriate, with a type 1 error of 0.05. Additionally, we will use linear regression to adjust for differences in baseline characteristics.

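### The exploratory trend models choose covariates by observed baseline differences between arms, a rule that does not select for prognosis; a list fixed in advance, with site and the other strata, would be better.

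*Combined protocol and SAP*

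**What the plan says.** Section 10.6 has a 'Trends in endpoints' paragraph for each trial. For chronic pain, endpoints at baseline, 1, 3 and 6 months are compared in the CYP2D6 IM/PM subgroup "using a repeated-measures mixed effect model or generalized repeated-measures mixed effect model, as appropriate". Because participants are randomised to arm and not to the subgroup, the plan says that "there could be important differences in baseline characteristics between the two groups". It therefore adds models that "account for differences in baseline characteristics that differ between the Intervention" and Control subgroups. The acute pain paragraph has the same rule, "covariate-adjusted repeated measures mixed models that will account for differences in baseline characteristics that differ", and the depression paragraph repeats it.

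The candidates are open-ended. For chronic pain: "Potential baseline characteristics may include age, sex, income, education, insurance, and medical conditions". Acute pain names surgical procedure type instead of medical conditions. No test, threshold or fixed set is given.

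Section 4.1 says: "Randomization will be stratified by trial and site or clinic with a random block size within each site or clinic". It adds that "the randomization for the chronic pain trial will be stratified by presence/absence of depression", and that acute pain and depression are stratified by pediatric/adult. Neither site or clinic nor the chronic pain depression stratum is named as a candidate. Age, which is named, partly covers pediatric/adult.

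Section 10.8 calls the repeated-measures analyses exploratory. Sections 10.2 and 10.6 defer detail to separate SAPs, which are not among these documents.

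**The concern.** Adjustment in a randomised comparison gains precision from variables that predict outcome. Selecting on imbalance asks a different question, and the answer is unrelated to prognostic strength. Three things follow:

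- The model is unknown until the data are seen and may differ between the three trials.
- A strongly prognostic variable is no more likely to be picked than an irrelevant one.
- Strata balanced by design are the least likely to be picked, although they were thought important enough to stratify on.

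The reason given for the rule is also weaker than it looks. Section 7.4 places DNA sampling before randomisation, and genotype itself cannot be changed by arm. For the genotype-defined part of the subgroup, baseline differences between arms are therefore chance.

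At stake is precision in the trend analyses, and whether they can be called pre-specified.

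**Working it through.** **Inputs from the plan.** Section 10.1, chronic pain: effect size 0.40, 134 per arm, 90% power, two-sided alpha 0.049. Section 10.6: six named candidates. Synopsis: "11 sites with approximately 60-80 clinics" across the three trials.

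**Assumed inputs.** The threshold for 'differ' (p<0.05, with p<0.20 as a looser alternative), the correlation r of a covariate with outcome, and R² for a set of covariates. The documents give none of these.

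**1. The plan's own figure.** A two-sample t-test with d = 0.40 and alpha 0.049 has 90.2% power at 134 per arm and falls just short of 90% at 133. Then 134/0.30 = 447 per arm, 894 in total, and 894/0.90 = 994 randomised. The plan's figures reproduce. It gives no figure for the trend model.

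**2. How often a covariate is picked.** Under randomisation, a test at p<0.05 picks any one covariate 5% of the time, so a prognostic one is omitted 95% of the time (80% at p<0.20). With one prognostic and five irrelevant candidates, assumed independent, the chance of at least one irrelevant pick is 1 − 0.95⁵ = 23% (1 − 0.80⁵ = 67% at p<0.20).

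**3. How often a stratum is picked.** Phenotype is not a stratum, so balance carries into the subgroup only in part. Simulation puts the imbalance variance at 0.81, 0.71 and 0.60 of the unstratified value when 18%, 30% and 40% are actionable. For chronic pain the cut-off becomes 1.96/√0.71 = 2.33, which gives about 2% instead of 5%.

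**4. Variance penalty for one prognostic covariate.** Let Z be its standardised imbalance and c the cut-off. In units of 2σ²/n, the arm-effect variance is 1 − r² if the covariate is always in the model. Under the rule it is (1 − r²) + r²k, where k = E[Z²; |Z|<c] = (1 − α) − 2cφ(c).

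- p<0.05: k = 0.95 − 2 × 1.96 × 0.0584 = 0.72.
- p<0.20: k = 0.80 − 2 × 1.28 × 0.1755 = 0.35.

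The penalty is k·r²/(1 − r²):

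| r | r²/(1 − r²) | p<0.05 | p<0.20 |
|---|---|---|---|
| 0.1 | 0.010 | 0.7% | 0.4% |
| 0.2 | 0.042 | 3% | 1.5% |
| 0.3 | 0.099 | 7% | 3.5% |
| 0.5 | 0.333 | 24% | 12% |

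Simulation at r = 0.5 and p<0.05 with six candidates gave 22% (134 per arm) and 25% (271 per arm).

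**5. A whole list.** Simulation with 134 per arm, six equally prognostic covariates (one a balanced stratum), effect 0.40, alpha 0.05, and selection at p<0.05:

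| R² | SE, selected | SE, fixed | Power, selected | Power, fixed |
|---|---|---|---|---|
| 0 | 0.122 | 0.123 | 90.5% | 90.1% |
| 0.10 | 0.122 | 0.117 | 91.1% | 93.0% |
| 0.20 | 0.122 | 0.110 | 91.9% | 95.4% |
| 0.30 | 0.122 | 0.103 | 91.9% | 97.0% |

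No covariate was picked in about 77% of trials. With no true effect and R² = 0.20, the imbalance rule rejected in 4.3% of trials.

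**6. How to enter site or clinic.** In 268 participants, with R² of 0.10 from covariates and 0.05 from strata, adding strata as fixed effects gave an SE, relative to unadjusted, of 0.95 with 11 sites, 0.98 with 30 strata and 1.05 with 70 clinics. With nothing prognostic the ratios were 1.03, 1.06 and 1.14.

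**The case against.** **Little depends on it.** The primary tests in Section 10.4 and the secondary tests in Section 10.5 are two-sample comparisons without covariates. This stands. A reader might infer that the rule threatens the trials' main conclusions or inflates false positives. The documents do not support the first, and the simulated rejection rate of 4.3% speaks against the second.

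**The SAPs may fix the list.** They may, but Section 10.6 states a rule and does not merely leave a gap, so a SAP with a fixed list would depart from it.

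**The subgroup is not defined by genotype alone.** This stands in part. Section 10.3 includes pheno-converted participants. In chronic pain, Section 10.1 expects 10-15% actionable by genotype and a further 20% by drug interaction. Section 10.7 has Control phenotypes determined around the 6-month assessment, and the protocol does not date the inhibitor assessment. The pheno-converted part is therefore fixed before randomisation only if baseline medications define it. It would be too strong to say that every baseline difference in the subgroup must be chance. Selecting covariates by imbalance would not cure a subgroup shaped by post-randomisation prescribing.

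**The size rests on assumptions.** This stands. Both the threshold and r are assumed, and 22-25% applies only at r = 0.5. Where raw scores are modelled with baseline as a time point, the baseline outcome is already used, leaving less for other covariates to explain. That does not help the chronic pain endpoints of pain control and pain reduction. Section 11.2 defines them as a difference from and a ratio to baseline, so they are constant at baseline.

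**Adding strata is not always more precise.** This also stands: 60-80 clinic fixed effects could raise the SE.

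**Conclusion.** The point holds as a minor improvement to exploratory analyses. The rule does not select for prognosis, makes the model depend on the data, and will rarely pick the balanced strata.

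Under an assumed p<0.05 rule, a given prognostic covariate is omitted about 95% of the time, at a variance cost of about 3%, 7% and 22-25% for r of 0.2, 0.3 and 0.5. At least one of five irrelevant candidates enters in about 23% of trials. A looser threshold roughly halves the variance cost.

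A reader might infer that a fixed list is more precise in every case. It is not: the gain requires prognostic covariates and a sparing treatment of site or clinic. If nothing is prognostic there is no gain.

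**What to change.** In the three 'Trends in endpoints' paragraphs and the SAPs, replace selection by observed differences with a list fixed in advance and used whatever imbalance is seen:

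- **All trials:** site, or clinic as a random effect (not 60-80 fixed effects), age and sex.
- **Acute pain:** also pediatric/adult and surgical procedure type.
- **Chronic pain:** also the depression stratum.
- **Depression:** also pediatric/adult.

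Add the baseline score where it is collected and not already modelled as a time point. This matters most for baseline pain intensity with the chronic pain change and ratio endpoints. It cannot be done for acute pain opioid usage, which Section 7.3 and Table 8 collect only at 10 days and 1 month.

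The cost is wording, with no new data collection. The analysis spends a few degrees of freedom, with a negligible loss if the covariates are not prognostic (SE 0.123 against 0.122 in the simulation at R² = 0, six covariates). Entering 11 sites as fixed effects as well raises the SE by about 3% in that case.
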